## **12.0 Withdrawal of Subjects**

*12.1 Describe anticipated circumstances under which subjects will be withdrawn from the research without their consent.*

Response: A subject may be withdrawn from the study if they are having significant side effects to liraglutide – nausea/vomiting, severe hypoglycemia. In addition, a subject may be withdrawn if they are having difficulty completing the study tasks essential for data collection.

*12.2 Describe any procedures for orderly termination.*

Response: Subject data will not be included in the analysis, and the subject will be replaced. All subjects will receive study compensation even if they are not included in the final study analysis.

*12.3 Describe procedures that will be followed when subjects withdraw from the research, including partial withdrawal from procedures with continued data collection.*

Response: If a subject is withdrawn from the research prior to de-identification of data, no data will be used for the subject. The data will be expunged and the subject will be replaced. If a subject withdraws from the study after de-identification of data, no further data will be collected for that subject. However, any data already collected may be included in the final analysis.

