## **11.0 Provisions to Monitor the Data and Ensure the Safety of Subjects**

*11.1 Describe the plan to periodically evaluate the data collected regarding both harms and benefits to determine whether subjects remain safe.*

Response: [name] is responsible for review of data on a regular basis to ensure that collected data is being entered correctly. All unforeseen events during the study tasks will be reported immediately to the principal investigator; if necessary, they will be reported to the IRB.

*11.2 Describe what data are reviewed, including safety data, untoward events, and efficacy data.*

Response: Data related to study tasks will be reviewed.

*11.3 Describe how the safety information will be collected (e.g., with case report forms, at study visits, by telephone calls with participants).*

Response: Safety information will be documented on the data collection tool as necessary.

*11.4 Describe the frequency of data collection, including when safety data collection starts.*

Response: [name] is responsible for collection and review of all data.

*11.5 Describe who will review the data.*

Response: [name]

*11.6 Describe the frequency or periodicity of review of cumulative data.*

Response: see above

*11.7 Describe the statistical tests for analyzing the safety data to determine whether harm is occurring.*

Response: Number of severe hypoglycemic events will be documented. The rate of severe hypoglycemia will be compared to historical data.

*11.8 Describe any conditions that trigger an immediate suspension of the research.*

Response: Episode of pancreatitis.

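### Withdrawn subjects are dropped and replaced with no exception for safety data, so a withdrawal for nausea/vomiting or severe hypoglycemia would lower the reported proportion of subjects affected

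*Combined protocol and SAP*

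**What the plan says.** Section 12.1 concerns withdrawal by the study team: "A subject may be withdrawn from the study if they are having significant side effects to liraglutide", with nausea/vomiting and severe hypoglycemia as the named examples. Difficulty with the study tasks is a further ground.

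Section 12.2 sets the data rule: "Subject data will not be included in the analysis, and the subject will be replaced". It continues: "All subjects will receive study compensation even if they are not included in the final study analysis".

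Section 12.3 divides cases by de-identification. Before it, "no data will be used for the subject", and then: "The data will be expunged and the subject will be replaced". For a subject who withdraws after it, collection stops, with this allowance: "However, any data already collected may be included in the final analysis".

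The events named in 12.1 are also outcomes. Section 7.0 lists nausea/vomiting and rates of hypoglycemia among the safety endpoints. Exploratory Aim 1 (Section 1.3) reports the kind, count and rate of adverse events. Section 11.7 says "Number of severe hypoglycemic events will be documented" and "The rate of severe hypoglycemia will be compared to historical data".

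No section defines a safety population.

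**The concern.** Under 12.1 and 12.2 taken together, having the event can cause a subject to be left out of the count of that event. A subject withdrawn for severe hypoglycemia leaves both numerator and denominator and is replaced by someone else. A subject who has the event and stays in is counted. The cases most likely to disappear are those serious enough to end participation.

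At stake are the side-effect profile under Exploratory Aim 1 and the severe-hypoglycemia rate taken to the historical comparison. Section 14.1 says the results may be used to develop longer randomized trials, so the tolerability profile has a planned use. With at most 12 subjects, one missing case can turn one event into none.

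**Working it through.** **The plan's own figure.** The only computed figure is the sample size in 10.2. With a difference of 22 mg/dL, an SD of the paired difference of 20 mg/dL and two-sided alpha 0.05, the paired t-test has 76.1% power at n = 8 and 82.3% at n = 9. The stated 9 subjects reproduce. This point does not depend on that figure; it uses only the enrolment limit of 12 (10.2, 22.1).

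**Inputs.** The documents give no event or withdrawal rate, so all counts below are assumed. Let N be the completers, x the completers with the event, and w the subjects withdrawn for it. Assume no withdrawals for other reasons.

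**Proportion of subjects affected.** Reported: x/N. All dosed subjects: (x + w)/(N + w). The shortfall is

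(x + w)/(N + w) − x/N = w(N − x)/[N(N + w)].

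This is positive whenever w ≥ 1 and x < N. It is zero if w = 0 or if every completer had the event.

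| N, x, w | All dosed (exact 95% CI) | Reported (exact 95% CI) | Shortfall, points |
|---|---|---|---|
| 12, 0, 1 | 1/13 = 7.7% (0.2–36.0%) | 0/12 = 0% (0–26.5%) | 7.7 |
| 12, 0, 2 | 2/14 = 14.3% (1.8–42.8%) | 0/12 = 0% (0–26.5%) | 14.3 |
| 12, 3, 1 | 4/13 = 30.8% (9.1–61.4%) | 3/12 = 25.0% (5.5–57.2%) | 5.8 |
| 11, 0, 1 | 1/12 = 8.3% (0.2–38.5%) | 0/11 = 0% (0–28.5%) | 8.3 |
| 10, 0, 2 | 2/12 = 16.7% (2.1–48.4%) | 0/10 = 0% (0–30.8%) | 16.7 |

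The first three rows let replacements go beyond 12. The last two treat 12 as a cap that includes the withdrawn subjects. The plan does not say which applies.

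**In expectation.** If a subject has the event with probability p, and an affected subject is withdrawn with probability q, the expected reported proportion is p(1 − q)/(1 − pq). With p = 0.10 and q = 0.5: 0.05/0.95 = 5.3%. With p = 0.20 and q = 0.5: 0.10/0.90 = 11.1%. With p = 0.40 and q = 0.25: 0.30/0.90 = 33.3%. The chance of at least one such withdrawal among 12 dosed subjects is 1 − (1 − pq)^12: 14% at p = 0.05, q = 0.25, and 72% at p = 0.20, q = 0.5.

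**Events per person-time.** Dropping a subject lowers this rate only if that subject's own rate exceeds the completers' rate.

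- Rare event: 12 completers with none over 12 × 7 = 84 days, and one subject withdrawn on day 3 with one event. All dosed: 1/87 = 0.011 per day. Reported: 0/84 = 0. The shift is downward.
- Frequent event: completers average 4 events in 7 days, 48/84 = 0.571 per day. The withdrawn subject has 1 in 3 days (0.33 per day). All dosed: 49/87 = 0.563. Reported: 0.571. The shift is slightly upward.

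**The case against.** The strongest reply is that the exclusion in 12.2 was meant for efficacy only. The analysis plan in 10.1 contains no adverse-event analysis; safety sits separately in 11.7. Section 11.7 has severe hypoglycemic events documented, and 13.1 makes the investigators responsible for recording adverse events and keeping them in the study record. This reading is possible, but it is not stated. Section 12.2 goes on to speak of the final study analysis without restriction, and 12.3 bars any use of the data and calls for expunging. A duty to record an event does not put the subject into a rate.

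The second reply is that 12.3 lets some data survive. Section 8.5 describes transfer to a spreadsheet without identifiers, and 10.5 calls for timely entry. Data entered before withdrawal might therefore count as de-identified and be kept. That is a fair reading, so it would go too far to say that the documents offer no route to retention. But the allowance is optional, is worded for a subject who withdraws, and conflicts with the unconditional exclusion in 12.2. No section names the point at which de-identification takes place.

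The third reply is that this is a small, unblinded one-week pilot whose side-effect profile is exploratory, and that 22.2 expects everyone to finish. This stands as a limit on the size. It does not justify the rule, since Section 12.0 itself plans for withdrawals.

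**Conclusion.** The point holds conditionally. If a subject is withdrawn for nausea/vomiting or severe hypoglycemia and 12.2 is applied as written, the reported proportion of subjects affected is too low, provided at least one completer did not have the event. With one such withdrawal and no affected completers, the shortfall is about 8 percentage points. With no withdrawals it is nil. The intervals overlap widely, so the problem is a systematic loss of the more serious cases and would not show up as a detectable difference.

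This rests on assumed counts, on reading the 12.2 exclusion as covering safety data, and on no other withdrawals. Event-free subjects dropped for difficulty with study tasks would push the proportion the other way.

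A reader might infer three stronger things that the documents do not support:

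- **That every safety rate must be biased downward.** The endpoints speak of rates and numbers without fixing the scale, and the person-time example shows that the direction can reverse for a frequent event.
- **That the historical comparison would reach a wrong conclusion.** No historical rate or decision rule is given, so that effect cannot be sized.
- **That the weekly glucose result is biased in a known direction.** It would be a completers-only estimate, but the direction is unknown and the matter is secondary here.

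**What to change.** Change only the data-handling wording of 12.2 and 12.3; leave 12.1 unchanged.

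1. State that every subject who receives at least one liraglutide dose is in the safety analysis, with events and exposure counted to last contact.
2. State that exclusion, expunging and replacement apply to the efficacy analysis only and not to safety data already collected, subject to the consent terms (those pages were not available for this review).
3. State that replacements add to the safety denominator, and whether they count toward the 12.
4. Report all withdrawals with their reasons.
5. Say when de-identification takes place, and reconcile 12.2 with 12.3 and both with 8.5, 10.5, 11.1, 11.7 and 13.1.

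For events already known to the study team, the cost is wording only. The treatment-week diary is returned at Visit 3 (8.2) and no early-termination contact is described, so diary data still with a withdrawn subject would need a retrieval step if wanted. Reported adverse-event rates may look less favourable. The change should be made before any withdrawal occurs, because expunged data may not be recoverable.

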- Insulin regimen and daily insulin use
- Other medications
- Side effect diary
- 4 day food records

In addition, the insulin pump download and blood glucose monitor downloads will be reviewed to collect the following information:

For all subjects:

- Number of blood sugar checks/day (average of 7 days prior to visit)
- Total basal dose
- Total daily insulin dose
- %basal/%bolus
- Boluses recorded/day
- Grams of carbohydrate recorded/day

Data will be recorded on the source document that carries the subject identifier number. Data will then be transferred to an Excel spreadsheet – no identifying data will be recorded in this spreadsheet.

*8.6 What data will be collected including long-term follow-up.*

*Response:* See above.

*8.7 For HUD uses provide a description of the device, a summary of how you propose to use the device, including a description of any screening procedures, the HUD procedure, and any patient follow-up visits, tests or procedures.*

*Response:* N/A

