## **10.0 Data Management**

*10.1 Describe the data analysis plan, including any statistical procedures.*

*Response:* For statistical purposes, the **primary endpoint** of the study is to detect a difference between untreated and treated periods in the change from baseline in mean weekly blood glucose concentrations. The statistical analysis will be carried out using analysis of variance (ANOVA) and tested at the 0.05 level. The results will be computed as mean±SD.

The secondary end points based on glycemic changes will include the difference from baseline in standard deviations of the mean weekly glucose concentrations, mean fasting blood glucose concentrations, the duration of time spent in hyperglycemia ( $>150\text{mg/dL}$ ,  $>200\text{mg/dL}$ ,  $>250\text{mg/dL}$ ) and hypoglycemia ( $<70\text{mg/dL}$ ,  $<40\text{mg/dL}$ ), and insulin dosage. A reduction in the area under curve following the meal will constitute another secondary end point. Within subject comparisons of the magnitude of change from baseline will also be made for these glycemia related secondary endpoints using student's t-test. Comparisons for these and the primary endpoints will also be made using the paired t-test or Wilcoxon's test for paired data for each subject. Additional secondary end-points of the study will be change from baseline in 1) mean weekly blood glucose 2) glucagon area under the curve concentrations following meal challenge 3) change in daily insulin dose (total dose and units/kg) 4) caloric intake based on 4 day food records and 5) change in serum adiponectin and CRP levels before and after initiation of liraglutide treatment. The relation between change in postprandial sugars, glucagon, and total daily insulin dose will be studied by regression analysis to evaluate the relative contribution of each of these parameters to the improvement in post-prandial blood sugars

*10.2 Provide a power analysis.*

*Response:* A previous study (5) in adults with well-controlled diabetes demonstrated that liraglutide treatment decreased mean weekly blood sugars by 22 mg/dL. Based on these results, *a priori* power analysis indicates that 9 subjects will need to be enrolled in the study to detect a change in mean weekly blood sugars of  $22 \pm 20\text{ mg/dL}$  between untreated and treated periods with 80% power and alpha error of 0.05 (paired t-test). We will enroll up to 12 subjects for this study.

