## **22.0 Local Number of Subjects**

*22.1 Indicate the total number of subjects to be accrued locally.*

Response: 12

*22.2 If applicable, distinguish between the number of subjects who are expected to be enrolled and screened, and the number of subjects needed to complete the research procedures (i.e., numbers of subjects excluding screen failures.)*

Response: We expect that all subjects who meet inclusion/exclusion criteria and sign informed consent/assent will complete the study.

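### The withdrawal rules in 12.2 and 12.3 drop and replace dosed subjects for reasons tied to drug response and disagree on late withdrawals, so the primary result describes tolerating completers plus replacements

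*Combined protocol and SAP*

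**What the plan says.** Section 12.1 lists when the investigator may withdraw a subject: significant side effects of liraglutide, with nausea/vomiting and severe hypoglycemia named, and also that "a subject may be withdrawn if they are having difficulty completing the study tasks essential for data collection".

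Section 12.2, on orderly termination, then states without any timing condition: "Subject data will not be included in the analysis, and the subject will be replaced".

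Section 12.3 makes the answer depend on de-identification. For a subject who is withdrawn before it, no data are used, the data are expunged and the subject is replaced. For a subject who withdraws after it, collection stops. It then adds: "However, any data already collected may be included in the final analysis". Nobody is assigned that choice and no criterion is given.

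The date of de-identification is not stated. Section 23.1 says only that study data will be de-identified. The nearest procedural text is in 8.5: "Data will then be transferred to an Excel spreadsheet", with no identifying data in the sheet.

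Sections 7.1 and 10.1 define the primary comparison of mean weekly glucose between the untreated and treated weeks. They give no analysis population, no missing-data rule and no minimum amount of CGM data. On completion, 22.2 says: "We expect that all subjects who meet inclusion/exclusion criteria and sign informed consent/assent will complete the study".

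**The concern.** The hypothesis in 1.2 is about adolescents and young adults with Type 1 diabetes treated with liraglutide. Under 12.2, a subject who took the drug and was withdrawn because of it leaves the primary analysis, and someone else takes the place. Exclusion is then related to the response to treatment. In a within-subject study of at most 12, one subject is 1/12, or 8%, of the data.

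The direction of the resulting bias is not fixed. Severe hypoglycemia is a glucose outcome, and dropping those subjects would tend to remove falls in glucose, which is conservative for a claim of benefit. Dropping subjects whose glycemia was poor, for instance if they were counted as having difficulty with study tasks, would favour liraglutide. Nausea and vomiting may change food intake and so glucose.

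Sections 12.2 and 12.3 also cannot both be followed for a late withdrawal unless the words for being withdrawn and for withdrawing are taken to mean different things. With an undated trigger and an optional inclusion, two analysts could properly reach different analysis sets from the same records.

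**Working it through.** **The rules side by side**

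| Situation | 12.2 | 12.3 |
|---|---|---|
| Withdrawn by the investigator, before de-identification | excluded, replaced | not used, expunged, replaced |
| Withdrawn by the investigator, after de-identification | excluded, replaced | inclusion optional, if withdrawing covers this case |
| Subject leaves by choice, before de-identification | not clearly covered | not literally covered |
| Subject leaves by choice, after de-identification | not clearly covered | inclusion optional |

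Only the first row has one clear answer, and that answer is exclusion.

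**Inputs.** From 10.2: "liraglutide treatment decreased mean weekly blood sugars by 22 mg/dL" in the earlier adult study; planned change 22 ± 20 mg/dL, read here as mean and SD of the paired difference; 80% power; alpha 0.05, taken as two-sided; paired t-test; 9 subjects needed; and "We will enroll up to 12 subjects for this study". The documents give no withdrawal rate, so every withdrawal count below is an assumption.

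**The plan's own figure.** Standardized effect = 22/20 = 1.10. Exact paired-t power (noncentral t) is 76.1% at n = 8 and 82.3% at n = 9, so the stated 9 is reproduced. At n = 12 power is 93.3%. The sample size is not in dispute.

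**Shift in the estimate.** If k of 12 dosed subjects are dropped and their mean change differs from the rest by d, the analysed mean differs from the mean in all dosed subjects by (k/12) × d.

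- k = 2, d = 20 mg/dL (1 SD): (2/12) × 20 = 3.3 mg/dL; 3.3/22 = 15%.
- k = 2, d = 40 mg/dL: (2/12) × 40 = 6.7 mg/dL; 6.7/22 = 30%.

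**Error rate with no true effect.** Simulation of 400,000 trials: changes normal with mean 0 and SD 20, two-sided t-test at 5%, selected subjects replaced by fresh draws.

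| Who is replaced | n | One replaced | Two replaced |
|---|---|---|---|
| Least favourable outcome, known exactly | 12 | about 9.3% | about 15.8% |
| Least favourable outcome, known exactly | 9 | about 9.5% | about 15.5% |
| Least favourable on a marker correlated 0.5 with outcome (assumed) | 12 | about 5.9% | about 7.0% |

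The first two rows are an outer bound, since they require the extreme outcome to be known and removed.

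**Opposite direction.** Replacing the subject with the largest fall (n = 12, exact knowledge) cuts false findings of benefit from the nominal 2.5% to 1.3%. Replacing the subject with the least favourable change raises them to about 8%.

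**The case against.** The strongest reply is that this is a small unblinded pilot that expects no withdrawals; if none occur, the rules never operate and there is no bias. That stands as a limit on expected size. It does not remove the rule, since section 12.0 itself plans for exclusion and replacement, and 7.1 plans a test at the 0.05 level.

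Several stronger readings are tempting and are not supported:

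- A reader might infer that staff watch treated-week glucose and choose whom to drop. Section 8.2 has treated-week CGM data obtained at Visit 3; before then, subjects are asked to report persistent lows, persistent highs or ketones. Staff may learn something about glycemia, but the documents do not show that they hold the primary outcome at a mid-week withdrawal.
- A reader might equate de-identification with the transfer to the spreadsheet. No section says so. The supportable point is that the step has no date.
- A reader might treat the optional inclusion in 12.3 as the main route to bias. A subject who leaves before Visit 3 would normally have only untreated-week CGM data on file, so the option reaches the paired change mainly in late withdrawals. Exclusion and replacement in 12.2 matters more.
- A reader might conclude that inclusion depends on who initiated withdrawal. That rests on section order and on a difference in verb form. If the two verbs mean the same, the sections simply conflict for late withdrawals.
- A reader might say that nothing can be checked afterwards. Expunging applies only in one branch of 12.3, and 10.5 has meter and pump downloads scanned into the medical record.

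**Conclusion.** The point holds as a defect in the analysis rule. Sections 12.2 and 12.3 need to be reconciled, and as written they yield a mean change in tolerating completers plus replacements.

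The size is conditional. With 2 of 12 dropped and a 20 mg/dL difference, the estimate moves by 3.3 mg/dL, 15% of the planned effect; with no withdrawals it does not move. The two-sided error is about 6% with one replaced subject and 7% with two, if withdrawal follows a marker correlated 0.5 with outcome. Error rates of 9 to 16% should be read only as an outer bound. They select the least favourable outcome, whereas the one withdrawal ground that is itself a glucose event, severe hypoglycemia, would tend to act the other way. The direction of bias therefore cannot be stated in advance.

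All figures rest on an SD of 20 mg/dL for the change, normal differences and assumed withdrawal counts.

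**What to change.** Replace the data-handling text of 12.2 and 12.3 by one analysis rule fixed in advance, and repeat it in 10.1:

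- Every subject who receives a first dose and has treated-week CGM data meeting a prespecified minimum stays in the primary analysis. State the minimum, and whether days after stopping the drug count.
- The rule applies whoever initiated the withdrawal and whenever the data were de-identified. The exceptions are a subject's own request for data removal, or a requirement of the consent terms, which should be checked before the wording is settled.
- Replacements may be added but displace no dosed subject. State whether they count toward the 12.
- Report the number of withdrawals and replacements with reasons, and a completers-only analysis as sensitivity.

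The clinical grounds for withdrawal in 12.1 are not touched. The cost is an amendment, with a check that the consent wording agrees, and no new procedures. Partial weeks will make some subjects' means noisier, and the estimate may be slightly less favourable.
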